10.15 Publication and Disclosure Policy

All information regarding ospemifene supplied by the Sponsor to the Investigator is privileged and confidential. The Investigator agrees to use this information to accomplish the study and will not use it for other purposes without consent from the Sponsor. It is understood that there is an obligation to provide the Sponsor with complete data obtained during the study. The information obtained from the clinical trial will be used toward the development of ospemifene and may be disclosed to regulatory authority(ies), other Investigators, corporate partners, or consultants as required.

The Sponsor will retain ownership of all data. All proposed publications based on the study will be subject to the Sponsor's approval requirements.

The key design elements of this protocol will be posted in a publicly accessible database, eg, ClinicalTrials.gov.

10.16 Financial Disclosure

Information concerning financial disclosure for Investigators will be addressed in a separate agreement between the Sponsor and the Investigator.

In accordance with the applicable regulations (21 CFR Parts 54, 312, 314, 320, 330, 601, 807, 812, 814, and 860), the Sponsor will provide the FDA with: Certification, that no financial arrangements with an Investigator or Sub-investigator have been made where compensation could affect study outcome; that the Investigator or Sub-investigator has no proprietary interest in the tested product; that the Investigator or Sub-investigator does not have a significant equity interest in the Sponsor of the covered study; and that the Investigator has not received significant payments of other sorts, and/or disclosure of specified financial arrangements and any steps taken to minimize the potential for bias.

Appendix 1 **Restricted Dietary and Herbal Therapies**

Soy (*Glycine max*)

Flaxseed (*Linum usitatissimum*)

Nettle root (*Urtica dioica*)

Pygeum (*Pygeum africanum*)

Beta-sitosterol

Licorice (*Glycyrrhiza glabra*)

Ginseng

Tribulus (*Tribulus terrestris*)

Red clover (*Trifolium pretense*)

Chasteberry (*Vitex agnus-castus*)

Japanese knotweed (*Polygonum cuspidatum*)

Black Cohosh (*Cimicifuga racemosa*)

Hops (*Humulus lupulus*)

Dong Quai (*Angelica sinensis*)

Fo-Ti (*Polygonum multiflorum*)

Kudzu (*Pueraria lobata*)

Alfalfa (*Medicago sativa*)

Mung bean sprout (*Vigna radiata*)

Sicklepod (*Cassia obtusifolia*)

Turkish rhubarb root (*Rheum palmatum*)

Phytoestrogens:

- Isoflavones (biochanin A, daidzein, genistein)
- Resveratrol
- Coumestrol

Appendix 2 Patient Self-Assessment of Vulvar and Vaginal Atrophy Questionnaire

*Have you had the following symptoms in the past month? (or since the last visit?)
If yes, please indicate if the most severe episode of the symptom was mild, moderate or severe.
Please choose one option per question.*

| Symptom | None | Mild | Moderate | Severe |
|---|------|------|----------|--------|
| Vaginal Dryness? | | | | |
| Vaginal and/or Vulvar Irritation or Itching? | | | | |
| Difficult or Painful Urination? | | | | |
| Vaginal Pain Associated with Sexual Activity? | | | | |
| Vaginal Bleeding Associated with Sexual Activity? | | | | |

| | |
|---|--|
| Which symptom is the most bothersome to you? Please choose one symptom that was indicated above as moderate or severe. (Ask at Visits 1 and 2 [Screening & Randomization]) | |
| Vaginal Dryness? | |
| Vaginal and/or Vulvar Irritation or Itching? | |
| Difficult or Painful Urination? | |
| Vaginal Pain Associated with Sexual Activity? | |
| Vaginal Bleeding Associated with Sexual Activity? | |

[figure not shown]
Appendix 3 Vaginal Health Index (VHI)

| | 1 | 2 | 3 | 4 | 5 |
|---------------------------|--------------------------|---------------------------|----------------------|--------------------------|----------------------------|
| Overall Elasticity | None | Poor | Fair | Good | Excellent |
| Fluid Secretion | None | Scant | Superficial | Moderate | Normal |
| pH | ≥ 6.1 | 5.6–6.0 | 5.1–5.5 | 4.7–5.0 | ≤ 4.6 |
| Epithelial Mucosa | Petechiae before contact | Bleeds with light contact | Bleeds with scraping | Not friable, thin mucosa | Not friable, normal mucosa |
| Moisture | None, mucosa inflamed | None, mucosa not inflamed | Minimal | Moderate | Normal |

Appendix 4 Vulvar Health Index (VuHI)

| | Normal (0) | Mild (1) | Moderate (2) | Severe (3) |
|--|-------------------|---------------------------|-------------------------------|---|
| Labia Majora | Normal | Mild loss | Moderate loss | Severe loss or disappeared |
| Labia Minora | Normal | Mild loss | Moderate loss | Severe loss or disappeared |
| Clitoris | Normal size | Mild decrease in size | Moderate decrease in size | Severe decrease or undetected |
| Introitus & Elasticity | Normal | Mild decrease or stenosis | Moderate decrease or stenosis | Severe decrease or stenosis |
| Color | Normal | Mild pallor | Moderate pallor | Severe pallor |
| Discomfort & Pain | None | Mild during intercourse | Moderate during intercourse | Moderate during intercourse and any discomfort intensity beyond intercourse |
| Other Findings (Petechiae, Excoriation, Ulceration, etc.) | None | Mild | Moderate | Severe |

Appendix 5 Process for Capturing Vulvar and Vaginal Photography

Appendix 6 **Female Sexual Function Index (FSFI) Questionnaire**

Subject ID _____ Date _____

INSTRUCTIONS: These questions ask about your sexual feelings and responses during the past 4 weeks. Please answer the following questions as honestly and clearly as possible. Your responses will be kept completely confidential. In answering these questions the following definitions apply:

Sexual activity can include caressing, foreplay, masturbation and vaginal intercourse.
Sexual intercourse is defined as penile penetration (entry) of the vagina.

Sexual stimulation includes situations like foreplay with a partner, self-stimulation (masturbation), or sexual fantasy.

CHECK ONLY ONE BOX PER QUESTION.

Sexual desire or interest is a feeling that includes wanting to have a sexual experience, feeling receptive to a partner's sexual initiation, and thinking or fantasizing about having sex.

1. Over the past 4 weeks, how **often** did you feel sexual desire or interest?
 - Almost always or always
 - Most times (more than half the time)
 - Sometimes (about half the time)
 - A few times (less than half the time)
 - Almost never or never

2. Over the past 4 weeks, how would you rate your **level** (degree) of sexual desire or interest?
 - Very high
 - High
 - Moderate
 - Low
 - Very low or none at all

Sexual arousal is a feeling that includes both physical and mental aspects of sexual excitement. It may include feelings of warmth or tingling in the genitals, lubrication (wetness), or muscle contractions.

3. Over the past 4 weeks, how **often** did you feel sexually aroused ("turned on") during sexual activity or intercourse?

- No sexual activity
- Almost always or always
- Most times (more than half the time)
- Sometimes (about half the time)
- A few times (less than half the time)
- Almost never or never

4. Over the past 4 weeks, how would you rate your **level** of sexual arousal ("turn on") during sexual activity or intercourse?

- No sexual activity
- Very high
- High
- Moderate
- Low
- Very low or none at all

5. Over the past 4 weeks, how **confident** were you about becoming sexually aroused during sexual activity or intercourse?

- No sexual activity
- Very high confidence
- High confidence
- Moderate confidence
- Low confidence
- Very low or no confidence

6. Over the past 4 weeks, how **often** have you been satisfied with your arousal (excitement) during sexual activity or intercourse?

- No sexual activity
- Almost always or always
- Most times (more than half the time)
- Sometimes (about half the time)
- A few times (less than half the time)
- Almost never or never

7. Over the past 4 weeks, how **often** did you become lubricated ("wet") during sexual activity or intercourse?

No sexual activity
 Almost always or always
 Most times (more than half the time)
 Sometimes (about half the time)
 A few times (less than half the time)
 Almost never or never

8. Over the past 4 weeks, how **difficult** was it to become lubricated ("wet") during sexual activity or intercourse?

No sexual activity
 Extremely difficult or impossible
 Very difficult
 Difficult
 Slightly difficult
 Not difficult

9. Over the past 4 weeks, how often did you **maintain** your lubrication ("wetness") until completion of sexual activity or intercourse?

No sexual activity
 Almost always or always
 Most times (more than half the time)
 Sometimes (about half the time)
 A few times (less than half the time)
 Almost never or never

10. Over the past 4 weeks, how **difficult** was it to maintain your lubrication ("wetness") until completion of sexual activity or intercourse?

No sexual activity
 Extremely difficult or impossible
 Very difficult
 Difficult
 Slightly difficult
 Not difficult

11. Over the past 4 weeks, when you had sexual stimulation or intercourse, how **often** did you reach orgasm (climax)?

No sexual activity
 Almost always or always
 Most times (more than half the time)
 Sometimes (about half the time)
 A few times (less than half the time)
 Almost never or never

12. Over the past 4 weeks, when you had sexual stimulation or intercourse, how **difficult** was it for you to reach orgasm (climax)?

No sexual activity
 Extremely difficult or impossible
 Very difficult
 Difficult
 Slightly difficult
 Not difficult

13. Over the past 4 weeks, how **satisfied** were you with your ability to reach orgasm (climax) during sexual activity or intercourse?

No sexual activity
 Very satisfied
 Moderately satisfied
 About equally satisfied and dissatisfied
 Moderately dissatisfied
 Very dissatisfied

14. Over the past 4 weeks, how **satisfied** have you been with the amount of emotional closeness during sexual activity between you and your partner?

No sexual activity
 Very satisfied
 Moderately satisfied
 About equally satisfied and dissatisfied
 Moderately dissatisfied
 Very dissatisfied

15. Over the past 4 weeks, how **satisfied** have you been with your sexual relationship with your partner?

Very satisfied
 Moderately satisfied
 About equally satisfied and dissatisfied
 Moderately dissatisfied
 Very dissatisfied

16. Over the past 4 weeks, how **satisfied** have you been with your overall sexual life?

Very satisfied
 Moderately satisfied
 About equally satisfied and dissatisfied
 Moderately dissatisfied
 Very dissatisfied

17. Over the past 4 weeks, how **often** did you experience discomfort or pain during vaginal penetration?

Did not attempt intercourse
 Almost always or always
 Most times (more than half the time)
 Sometimes (about half the time)
 A few times (less than half the time)
 Almost never or never

18. Over the past 4 weeks, how **often** did you experience discomfort or pain following vaginal penetration?

Did not attempt intercourse
 Almost always or always
 Most times (more than half the time)
 Sometimes (about half the time)
 A few times (less than half the time)
 Almost never or never

19. Over the past 4 weeks, how would you rate your **level** (degree) of discomfort or pain during or following vaginal penetration?

- Did not attempt intercourse
- Very high
- High
- Moderate
- Low
- Very low or none at all

Thank you for completing the questionnaire

Appendix 7 Urinary Distress Inventory (UDI-6)

Do you experience, and, if so, how much are you bothered by:

1. Frequent urination?

Yes No

If Yes, how much does it bother you?

not at all slightly moderately greatly

2. Urine leakage related to the feeling of urgency?

Yes No

If Yes, how much does it bother you?

not at all slightly moderately greatly

3. Urine leakage related to physical activity, coughing, or sneezing?

Yes No

If Yes, how much does it bother you?

not at all slightly moderately greatly

4. Small amounts of urine leakage (drops)?

Yes No

If Yes, how much does it bother you?

not at all slightly moderately greatly

5. Difficulty emptying your bladder?

Yes No

If Yes, how much does it bother you?

not at all slightly moderately greatly

6. Pain or discomfort in the lower abdominal or genital area?

Yes No

If Yes, how much does it bother you?

not at all slightly moderately greatly

Appendix 8 Genital Prolapse Grading

The following grading will be used for evaluation at screening (patient should have an empty bladder and Valsalva strain maximally).

[figure not shown]
Uterine Prolapse:

Grade 0 - Normally positioned cervix or vaginal apex
Grade 1 - Less than half way to the hymenal ring
Grade 2 - More than half way to the hymenal ring
Grade 3 - At the hymenal ring
Grade 4 - Halfway or greater outside the hymenal ring

Vaginal Prolapse (cysto[urethra]cele or rectocele):

Grade 0 - Normal
Grade 1 - Some bulging during Valsalva, no symptoms
Grade 2 - Size approximately hen's egg
Grade 3 - Approaching hymenal level, bulging "out"
Grade 4 - Clearly visible outside

Appendix 9 Diagnostic Procedures Required in a Subject with Intact Uterus and Vaginal Bleeding

Appendix 10 Management and Discontinuation Criteria for Abnormal Liver Function Tests

Management and Discontinuation Criteria for Abnormal Liver Function tests have been designed to ensure subject safety and evaluate liver event etiology. (See Guidance for Industry Drug-Induced Liver Injury: Premarketing Clinical Evaluation, Food and Drug Administration [FDA]: 2009)

1. Abnormal Liver Chemistry Criteria:

The Investigator or Sub-investigator must review study subject laboratories to identify if any levels meet the following criteria:

- a. AST or ALT $>5 \times$ ULN
- b. AST or ALT $>3 \times$ ULN and total bilirubin (TBL) $>2 \times$ ULN (SAE)
- c. AST or ALT $>3 \times$ ULN with signs or symptoms compatible with hepatitis or hypersensitivity (eg, fatigue, nausea, vomiting, right upper quadrant pain or tenderness, jaundice, fever, rash, eosinophilia [$>5\%$])

2. Action to be Taken by Investigator:

If any abnormal liver chemistry criterion is met, the Investigator or Sub-investigator must do the following:

- Subjects must be instructed to discontinue study medication immediately. The Investigator or Sub-investigator should not re-challenge the subject with the investigational product without consulting the Sponsor.
- Following the initial observed elevation, every effort should be made to have the subject return to the clinic within 72 hours to repeat liver function chemistries and for further hepatic evaluation.
- Every effort should be made to have the subjects must be monitored 2 to 3 times per week until liver function chemistries (ALT, AST, ALP, total bilirubin) resolve, stabilize or return to within the normal range or to baseline levels.
- This event must be reported to the Sponsor as soon as possible but no later than 24 hours of learning after its occurrence on the Liver Event Form.
- Consultation with a specialist such as a hepatologist is considered.
- Liver imaging (ie, ultrasound, magnetic resonance imaging (MRI), computerized tomography) is considered.
- For criteria b, termed “Hy’s law,” the case must be reported as an SAE.

[figure not shown]
3. Follow-up Examination:

If any of the abnormal liver chemistry criteria are met, the following assessments should be performed at the follow-up visit(s) and documented in the Liver Event Form:

[figure not shown]
- Clinical symptoms course
 - Concomitant medications: OTC (over-the-counter drug)/herbal/dietary supplements (start and stop dates)
- Alcohol use
- Risk factors for nonalcoholic steatohepatitis (NASH) such as diabetes, obesity and hypertriglyceridemia
- Autoimmune hepatitis/cholangitis
- Wilson's disease
- Laboratory Assessments
 - Viral hepatitis serology
 - Hepatitis A IgM antibody
 - Hepatitis B surface antigen (HBs antigen) and Hepatitis B core antibody (HBc antibody)
 - Hepatitis C RNA
 - Hepatitis E IgM antibody
 - Cytomegalovirus IgM antibody
 - Epstein-Barr viral capsid antigen IgM antibody
 - For subjects with total bilirubin of >1.5 ULN, conjugated bilirubin should be measured.
 - Complete blood count with differential to assess for eosinophilia

The Investigator or Sub-investigator must not re-challenge the subject with the investigational product without consulting the Sponsor.

Abnormal Liver Chemistry Criteria: Algorithm

Management and Discontinuation Criteria for Abnormal Liver Function Tests (LFT): Algorithm

1 INTRODUCTION

This “Statistical Analysis Plan” (SAP) presents details, including methods of analyses, of the efficacy and safety analyses described in Section 9 “Planned Statistical Methods” of the protocol [Protocol No. 1517I0231: 02 Nov, 2016] for the clinical trial entitled “A Phase 3, Randomized, Double-blind, Placebo-controlled Multicenter Study to Evaluate the Efficacy and Safety of Ospemifene in Patients with Moderate to Severe Vaginal Dryness, a Symptom of Vulvo-vaginal Atrophy (VVA) due to Menopause”.

Details of outputs (or mock-up of tables, listings, and figures) from analyses in this SAP will be included in a separate document (“Mock-up of Tables, Listings, and Figures”).

2 STUDY OVERVIEW

This is a multicenter, randomized, double-blind, placebo-controlled study to assess the efficacy and safety of ospemifene 60 mg once daily (QD) in postmenopausal women with vaginal dryness as the most bothersome symptom (MBS) of VVA due to menopause.

3 STUDY OBJECTIVES

The objective of this study is to evaluate the efficacy and safety of ospemifene 60 mg QD compared with placebo in treatment of VVA due to menopause in women with moderate to severe vaginal dryness as the MBS of VVA.

3.1 Primary Objectives

Objective 1: To assess the efficacy of ospemifene 60 mg daily at 12 weeks of treatment, relative to placebo, in the treatment of vaginal dryness, a symptom of vulvar and vaginal atrophy, due to menopause.

Hypothesis: After 12 weeks of treatment, ospemifene 60 mg QD, relative to placebo, significantly improves all 4 co-primary efficacy endpoints:

- Percentage of parabasal cells in the maturation index of the vaginal smear
- Percentage of superficial cells in the maturation index of the vaginal smear
- Vaginal pH
- Intensity of self-reported MBS of vaginal dryness

Objective 2: To assess the safety and tolerability of ospemifene 60 mg QD during 12 weeks of treatment, relative to placebo.

3.2 Secondary Objectives

Objective 1: To assess the effect of ospemifene 60 mg relative to placebo in change from baseline to Week 12 on:

- Severity of other VVA symptoms different from vaginal dryness (i.e., dyspareunia, vulvar/vaginal itching/irritation, dysuria [difficult/painful urination], vaginal bleeding associated with intercourse)
- Markers of bone metabolism
- Vaginal Health Index (VHI)
- Vulvar Health Index (VuHI)

Objective 2: To assess the effect of ospemifene 60 mg relative to placebo in change from baseline to Week 12 on:

- Female Sexual Function Index (FSFI)
- Urinary Distress Inventory (UDI-6)

Objective 3: To assess the effect of ospemifene 60 mg QD, relative to placebo, over 12 weeks on endometrial histology

4 STUDY DESIGN

4.1 Schedule

Schedule of time and events is presented in Appendix 1.

4.2 Study Blinding and Randomization

After screening, subjects who have $\leq 5\%$ superficial cells in the maturation index of the vaginal smear, a vaginal pH > 5.0 and vaginal dryness as MBS of VVA based on self-assessment, who also meet all other eligibility criteria, will be randomized in a 1:1 ratio to receive either ospemifene 60 mg QD or matching placebo for 12 weeks.

Randomization will be stratified by severity of MBS of vaginal dryness at Visit 2 and by the presence or absence of the uterus. Randomization of subjects without a uterus will be limited to 60% of the study population.

This study will be conducted in a double-blind manner using a placebo matching the test drug in appearance, labeling, and packaging. All subjects, the investigator, all study personnel, and the sponsor will be blinded to the treatment assigned at randomization until database lock.

4.3 Sample Size

Approximately 600 subjects, about 300 subjects per arm (1:1 randomization ratio), will be randomized in the study. A sample size of 600 subjects provides $\geq 90\%$ power for comparison between ospemifene 60mg and placebo in the 4 co-primary efficacy endpoints (changes from baseline to Week 12 in the percentage of parabasal cells, the percentage of superficial cells, the vaginal pH, and the intensity of MBS of vaginal dryness) with two sided significance level of 0.05.

5 ANALYSIS POPULATIONS

The following populations will be used for analyses.

- **Intent-to-Treat (ITT) Population** is defined as any subject that is randomized and receives at least one dose of study medication. All efficacy analyses will be based on this population. This population will be analyzed according to the treatment to which the subject was randomized. This population will be considered primary.
- **Modified ITT (mITT) Population** will include ITT subjects who had also met the following inclusion criteria:
 - 1) The subject had 5% or fewer superficial cells in the maturation index of the vaginal smear as baseline values. (Note that subjects with no baseline value for superficial cells will not be included in the mITT Population).
 - 2) The subject had vaginal pH > 5.0 as baseline values.
 - 3) The subject had moderate or severe vaginal dryness as baseline values and selected vaginal dryness as the most bothersome VVA symptom as baseline values.

This population will be used to analyze the primary efficacy endpoints and will be considered supportive.

- **Per-Protocol Population (PP)** will consist of all subjects in the mITT population who meet all of the following:
 - 1) Complete at least 10 weeks of treatment
 - 2) Take at least 85% of the study medication within 12 weeks
 - 3) Do not have any other major protocol deviation. Major protocol deviation will be reviewed to determine eligibility for the PP Population and finalized before breaking the study blind.
 - 4) Do not have a vaginal infection or any other medical condition that would confound the primary efficacy assessment.

This population will be used to analyze the primary efficacy endpoints and will be considered supportive.

- **Safety Population** includes all randomized subjects who receive at least one dose of the study medication. This population will be analyzed according to the treatment the subjects actually received rather than the treatment to which the subjects were randomized. If a subject takes both treatments, the subject will belong to the ospemifene group.

6 STATISTICAL CONSIDERATIONS FOR DATA ANALYSES AND HANDLING

6.1 Statistical Reporting

Unless otherwise noted, continuous variables will be summarized by using the number of non-missing observations, arithmetic mean, standard deviation (SD), median, minimum,

and maximum values as descriptive statistics; categorical variables will be summarized by using the frequency count and the percentage of subjects in each category as descriptive statistics.

In general, all tables will be presented by treatment group. Individual subject data and any derived data will be presented by treatment and subject. All analyses and tabulations will be performed by using SAS[®] Version 9.2 or higher.

6.2 Statistical Testing

All statistical tests will be performed at the 0.05 significance level using two-sided tests, except where otherwise noted.

6.3 Study Day and Analysis Windows

Day 1 is the initial dose date for subjects. Previous day to Day 1 is expressed as Day -1, and days before Day -1 in Screening Period are expressed as Day -2, Day -3, ... , etc.

Allowance window for each of the scheduled visits is shown in Table 1.

Allowance window for diary data is shown in Table 2.

If more than one visit occurs during a visit window, the one closest to the target day will be assigned to the visit. If two visits are equidistant from the target day, the latter visit will be assigned to the visit for post-baseline values.

If a subject discontinues from the study, the data obtained at early termination visit will be treated as one visit data based on the allowance windows.

Table 1 Definition of Visit Window

Scheduled Visit	Target Day	Window (Days)
Visit 1	Day -28	≤ Day -1
Visit 2 (Day 1)	Day 1(Randomization)	Day 1
Visit 3 (Week 4)	Day 29	Day 16 to Day 43
Visit 4 (Week 8)	Day 57	Day 44 to Day 71
Visit 5 (Week 12)	Day 85	Day 72 to Day 99
Early termination	Last dosing date	+ 14

Table 2 Definition of Diary Data Window

Week	Daily Data	Weekly Data (Target Day)
Week 1	Day 1 to Day 7	Day 4 to Day 10 (Day 7)
Week 2	Day 8 to Day 14	Day 11 to Day 17 (Day 14)
Week 3	Day 15 to Day 21	Day 18 to Day 24 (Day 21)
Week 4	Day 22 to Day 28	Day 25 to Day 31 (Day 28)
Week 5	Day 29 to Day 35	Day 32 to Day 38 (Day 35)

Week	Daily Data	Weekly Data (Target Day)
Week 6	Day 36 to Day 42	Day 39 to Day 45 (Day 42)
Week 7	Day 43 to Day 49	Day 46 to Day 52 (Day 49)
Week 8	Day 50 to Day 56	Day 53 to Day 59 (Day 56)
Week 9	Day 57 to Day 63	Day 60 to Day 66 (Day 63)
Week 10	Day 64 to Day 70	Day 67 to Day 73 (Day 70)
Week 11	Day 71 to Day 77	Day 74 to Day 80 (Day 77)
Week 12	Day 78 to Day 84	Day 81 to Day 87 (Day 84)

Assessments that occur more than 14 days after the last dose of study medication will be excluded from the above visit windows.

The baseline is defined as the last value that is observed prior to the first dose of study medication. For a variable that is planned to be observed at screening and randomization, the data at randomization will be used as baseline. For such variable, if the data at randomization is missing for a subject, the data observed at screening will be used as baseline.

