5.9 Treatment Compliance

The Investigator and/or study personnel will assess treatment compliance at each visit using pill counts and information provided by the subject. The Investigator should stress to the subject the importance of compliance and ensure that she understands the dosing instructions. Compliance checks by tablet count will be performed by qualified site

personnel in order to verify that the correct number of doses have been taken based on the actual number of days that have elapsed between designated clinic visits.

A record of the study drug taken by the subject will be made in the eCRF as required. In the event of discrepancy between the tablet count and the information provided by the subject, the information provided by the subject will be recorded in the eCRF.

Based on compliance checks, a subject will be counseled by the site about the importance of taking the study drug as directed if < 100% of the required study drug has been taken by that subject. If compliance issues persist and overall dosing compliance is < 80%, the Investigator may consider discontinuing the subject from the study.

In the event a subject has interrupted or discontinued study drug, the subject must inform the Investigator and the rationale must be provided in the source document. The subject may continue in the study after agreement with the Investigator. If the study drug has been temporarily discontinued for safety reasons, the Investigator must document the reasons in the source document and discuss with the medical monitor prior to the subject reinitiating study drug. All interruptions of study drug (≥ 1 day) should be captured in the eCRF.

In the event a subject is withdrawn for compliance reasons (eg, missed doses or visits), the Investigator will notify the Sponsor or designee promptly and will make every effort to complete the early termination assessments and the Completion/Discontinuation eCRF. The Investigator must register all subject discontinuations in the IxRS.

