9.4 Handling of Missing Data

Missing data will not be imputed. All analyses will be based on observed data.

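### The 14-day off-drug cut in SAP 6.3 applies to the primary ITT analysis, so some observed Week 12 values are dropped because the woman stopped drug, and no planned analysis shows the effect

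*SAP*

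**What the plan says.** SAP 6.3 sets the visit windows in Table 1. Week 12 has target Day 85 and runs from "Day 72 to Day 99". On women who leave the study the section says: "If a subject discontinues from the study, the data obtained at early termination visit will be treated as one visit data based on the allowance" (meaning those in Table 1). The Table 1 row for early termination reaches 14 days past the last dosing date. After the tables the section adds: "Assessments that occur more than 14 days after the last dose of study medication will be excluded from the above visit windows".

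SAP 5 makes ITT the primary population. It "is defined as any subject that is randomized and receives at least one dose of study medication", and "All efficacy analyses will be based on this population". On allocation, "This population will be analyzed according to the treatment to which the subject was randomized". Neither section exempts ITT from the 14-day rule.

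Protocol 5.9, on women who have interrupted or discontinued study drug, says: "The subject may continue in the study after agreement with the Investigator". Protocol 9.4 rules out imputation and adds: "All analyses will be based on observed data". Protocol 7.9 sets no visit windows. Protocol 8.5 repeats all four co-primary measures at early termination and gives no deadline after the last dose. SAP 13 lists one change from the protocol, a safety confidence-interval method.

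**The concern.** In an as-randomized analysis, whether a collected outcome counts should not depend on what happened to treatment after randomization. Here it can. A woman who stops on Day 60, stays in the study and attends on Day 85 has all four co-primary measures taken, and none of them enters the Week 12 comparison. Her values become missing and are not imputed.

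The models then rest on assumptions about those missing values. The MMRM needs them to be missing at random. The dryness GEE uses an independence working correlation without weights (SAP 9.1.2) and generally needs a stronger assumption: that missingness is unrelated to outcome given the covariates. Dryness also has the least power of the four endpoints, so it is the most exposed.

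No planned analysis would reveal a problem. The mITT and PP analyses use the same windows, and the only named sensitivity analysis (MMRM for dryness) uses the same data.

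**Working it through.** **1. What the rule removes.** An assessment on day *v* is excluded when *v* minus the last-dose day exceeds 14, that is, when the last dose was on or before day *v* − 15.

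| Visit day | Excluded if last dose on or before |
|---|---|
| 29 (Week 4 target) | Day 14 |
| 57 (Week 8 target) | Day 42 |
| 85 (Week 12 target) | Day 70 |
| 72 (Week 12 window opens) | Day 57 |
| 99 (Week 12 window closes) | Day 84 |

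- A last dose by Day 57 leaves no usable value anywhere in the Week 12 window.
- A termination visit on Day 76 is lost only if the last dose was on or before Day 61 (76 − 15).
- A woman whose last dose was by Day 14 and who attends on the target days keeps no post-baseline value. She still meets the ITT definition but contributes nothing to the models (opening of SAP 9).

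**2. Which analyses it changes.** PP requires at least 85% of study medication within 12 weeks. Taking 84 doses as the full course, a last dose by Day 70 allows at most 70/84 = 83%. Anyone whose Day 85 visit is excluded is therefore already outside PP. At the target visit the rule alters only the ITT and mITT results.

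**3. The plan's own power figure.** Inputs from protocol 9.2: 300 per arm, two-sided 0.05, dryness effect size 0.27. The noncentrality is effect size × √(n₁n₂/(n₁+n₂)), and the critical value is 1.964.

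0.27 × √150 = 3.307, which gives power 91.0%. The other three endpoints (0.70, 0.83, 0.68) are each near 100%, so joint power is about 91%. This agrees with the stated 90% or more.

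**4. Illustrative size for dryness.** The documents give no off-drug rate, so the share is an assumption. Suppose a share *d* of ospemifene women have Week 12 values caught by the rule, with true outcomes at placebo level.

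- Excluded: the effect stays 0.27, with 300(1 − *d*) against 300, recovering nothing from earlier visits.
- Retained: the effect is 0.27(1 − *d*), with 300 against 300 and the SD unchanged.

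| *d* | Excluded: n, noncentrality, power | Retained: effect, noncentrality, power |
|---|---|---|
| 2% | 294 v 300, 3.290, 90.7% | 0.265, 3.241, 89.9% |
| 4% | 288 v 300, 3.273, 90.4% | 0.259, 3.175, 88.7% |
| 6% | 282 v 300, 3.255, 90.1% | 0.254, 3.108, 87.4% |

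At 4% the like-for-like difference is about 0.01 in effect size and 90.4 − 88.7 = 1.7 points of power.

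The result depends on what happens off drug. With 10% affected in both arms, exclusion gives 270 per arm and 87.9%. Retention with no effect kept gives 0.27 × 0.90 = 0.243 and 84.4%. Retention with half the effect kept gives 0.27 × 0.95 = 0.2565 and 88.0%, so the difference in power all but vanishes.

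**The case against.** The strongest reply is that few women are affected. The paragraph in protocol 5.9 is largely about interruption, and resuming drug resets the last dose. Many women who stop for good will fall under protocol 7.7, which leads to early-termination assessments and 14 days of follow-up after the last dose. A termination visit within that time is kept. This stands: the rule mainly reaches late termination visits and women who stop for good but stay under 5.9, and that group may be small or empty.

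The cut also has a rationale. Fourteen days is the follow-up period, the adverse-event window and the early-termination limit in Table 1. A pre-specified on-treatment window is a legitimate choice of estimand. A reader might call the cut arbitrary, and the documents do not support that.

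The conflict with the protocol is arguable too. Protocol 9.4 concerns imputation and does not promise that every off-drug value enters a window. Protocol 9.1 leaves detailed methods to the SAP, so a window rule may count as detail. But 9.1 also asks for deviations to be specified with reasons, and no reason for this exclusion is given.

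None of this answers the remaining point: where such values exist, the primary ITT analysis discards them and nothing planned shows the effect.

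**Conclusion.** The point holds in a limited form. The 14-day rule lets stopping drug decide whether later observed values, above all those at Week 12, enter the primary ITT comparison, and no planned analysis tests this. It is a cheap improvement to make, and it does not invalidate the design. The stated power reproduces.

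Three stronger readings go too far:

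- **That women are removed from ITT.** The rule acts on assessments. Values up to 14 days after the last dose stay in the models.
- **That the excluded women stopped for adverse events or lack of benefit.** The documents give no reasons or rates for the women this rule would catch.
- **That the rule favours ospemifene.** The direction cannot be determined from the documents. Only if the effect fades off drug does exclusion give a larger estimate than all observed data.

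The 4% illustration rests on an assumed share, on placebo-level outcomes in those women, and on no information recovered from earlier visits. With no off-drug attenders the difference is nil.

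**What to change.** - **Add one pre-specified sensitivity analysis.** Analyse the four co-primary endpoints in the ITT population with the same MMRM and GEE models, using every assessment inside the Table 1 day windows regardless of time since last dose. Map termination visits by study day, so that the 14-day limit in the early-termination row does not bring the exclusion back.
- **State the 14-day rule and its reason in SAP 13.** The primary analysis can keep the rule if the on-treatment intent is made explicit. Confining the rule to PP would come close to deleting it, given step 2 of the working.
- **Reconcile protocol 5.9 with 5.5, 7.7 and 8.5** on who remains in the study after stopping drug, so that it is clear which women can supply such values.

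The cost is one extra run of existing models on data already collected, and a few sentences of text. The small downside is that the all-data estimate may be slightly less favourable.
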